8.2 Exclusion criteria

A patient will not be eligible for inclusion in this study if they meet any of the following criteria.

- Allergy to recombinant COVID-19 vaccine or any component of it
- Patient cannot or will not provide written informed consent.
- Unable to provide appropriate informed consent because of illiteracy or impairment in decision-making capacity.
- Active antibody-mediated or cellular rejection within the past six months
- Recent IBD flare requiring initiation of systemic corticosteroids within the past month
- Previous history of myocarditis or pericarditis ever.
- Patients who are pregnant
- Patients who are lactating
- Patients with an active COVID-19 infection
- Patients with a COVID-19 infection within the past two months

8.3 Subject Identification and Recruitment

Patients will be recruited from the University of Wisconsin Hospital and Clinics if they meet the inclusion criteria (see Section 8.0). Patients will be recruited in the following manner. Clinical research coordinators will prescreen provider clinic schedules (e.g. Clinics at the Digestive Health Center, Transplant Surgery, and etc.) and review medical records to evaluate potential study subjects that meet all inclusion criteria. The clinical research coordinator will review potential patients with the subspecialist who sees that patient. Any patient planning to receive a recombinant COVID-19 vaccine booster as standard of care will be invited to participate. Patients will be invited to participate after having any type of clinical contact with their provider or any member of their healthcare team. A member of the health team will provide patients with information about the study. The research coordinator will further review the information, invite participants to participate in the study, and obtain consent either in person or via remote consent.

If study team members are available, subjects would undergo an in-person consent discussion and be asked to sign a paper copy of the consent form. Alternatively, a member of the care team would obtain subject permission to allow study team members to contact the subject by phone for a follow-up discussion, and/or set up a virtual meeting using a HIPAA-compliant virtual platform, with subjects providing signed consent using an FDA part 11 compliant electronic signature (i.e., DocuSign).

Advertising (study flyers) will be posted throughout UW health entities such as the UW Digestive Health Center (DHC), 1 South Park, UW Hospital Ambulatory Center, Transplant Clinic, and other clinics throughout UW Health. These flyers will be used on TV screens in waiting room locations.

The study flyer will be shared through social media such as Twitter and tweeted by the PI, inviting patients to participate.

We will recruit participants via MyChart, UW Health's patient portal. Participants will be identified via a chart review by the Clinical Research Data Service (CRDS). We will obtain all needed approvals from UW Health and CRDS and follow the required workflows. We will/have create(d) an OnCore study record that is interfaced with Health Link and will track individual level recruitment in OnCore. Once approvals are in place, the IRB-approved invitation will be posted to invited participants' Research Studies page in MyChart and patients will initiate contact with study team if interested.

The patient-facing MyChart invitation is included with the IRB application for review and approval.

Patients will be recruited from the University of Wisconsin Hospital and Clinics if they meet the inclusion criteria (see Section 8.0). Patients will be recruited in the following manner. Clinical research coordinators will prescreen using Research Elecetronic Data Capture (REDCap) database system from provider clinics (e.g. Clinics at the Digestive Health Center, Transplant Surgery, etc.) and review medical records to evaluate potential study subjects that meet all inclusion criteria. The clinical research coordinator will review potential patients with the subspecialist who sees that patient. Any patient planning to receive a recombinant COVID-19 vaccine booster as standard of care will be invited to participate. Patients will be invited to participate after having any type of clinical contact with their provider or any member of their healthcare team. A member of the health team will provide patients with information about the study. The research coordinator will further review the information, invite participants to participate in the study, and obtain consent either in person or via remote consent.

A phone screening script will be used when contacting potential subjects by phone for recruitment or in person to the study flyer.

8.4 Remuneration for participation

Participants will be paid \$75 for each completed in-person study visit for a total up to \$75, \$150, and \$225, depending on the number of study visits. Payments will be made at the end of the study. If subjects choose to leave or are taken off the study before they complete it, they will receive payment for the visits completed.

8.5 Premature Subject Discontinuation

Patients will be encouraged to complete the study; however, they may voluntarily withdraw at any time.

The Principal Investigator may discontinue or withdraw a subject from the study for the following reasons at his/her discretion:

- Subject non-compliance with study requirements (e.g., study intervention non-compliance, do not complete scheduled visits)
- If any clinical adverse event (AE), laboratory abnormality, or other medical condition or situation occurs such that continued participation in the study would not be in the best interest of the subject

Subjects who sign the informed consent form but do not receive the study intervention will be replaced and will not be counted against the enrollment total. A one-to-one replacement will occur. Every patient who does not receive the study intervention will be replaced with another participant.

9.0 STUDY AGENT - NOVAVAX COVID-19 VACCINE, ADJUVANTED

The U.S. Food & Drug Administration (FDA) required an investigational new drug (IND) for the use of the Novavax Covid-19 Vaccine, Adjuvanted currently available under an Emergency Use Authorization (EUA).

9.1 Source

Study drug will be provided free of charge by the manufacturer, Novavax, for the study. Novavax will distribute the study drug to the study site. The University of Wisconsin Madison's Pharmaceutical Research Center (PRC) will be responsible for receipt of the product from the manufacturer.

Each shipment will include a temperature-monitoring device to verify maintenance of the cold chain during transit, as well as a packing slip. On delivery of the product to the site, the person in charge of product receipt will follow standard PRC instructions for receipt of product, including checking that the cold chain was maintained during shipment (i.e., verification of the temperature indicator). The contents of the shipment will then be reviewed and verified against the packing slip, and will be documented as instructed at the initiation visit.

If the temperature-monitoring indicator reflects that the cold chain has been broken, the entire shipment must be immediately quarantined and further processed consistent with PRC operating procedures.

9.2 Packaging and Labeling

The Novavax COVID-19 Vaccine, Adjuvanted will be obtained from the manufacturer in a multidose vial containing 5 or 10 doses of 0.5 mL each. Packages will be labeled with the statement "'Caution: New Drug—Limited by Federal (or United States) law to investigational use."

9.3 Preparation

The PRC will prepare the suspension for intramuscular injection as follows:

Inspection of the vial

- The Novavax COVID-19 Vaccine, Adjuvanted (Omicron XBB.1.5) NVX-CoV2601 is a colorless to slightly yellow, clear to mildly opalescent suspension, free from visible particles.
- The multi-dose vial will be gently swirled before each dose withdrawal. Do not shake.
- Each vial will be inspected visually for particulate matter and discoloration prior to administration, whenever solution and container permit. The vaccine will not be administered if either of these conditions exist.

Handling of Multidose Vial

- The date and time of the first puncture will be recorded on the vial label.
- After the first needle puncture, the vial will be held between 2 to 25°C (36 to 77°F) for up to 12 hours.
- The vial will be discarded 12 hours after the first puncture.

Handling of filled syringe

- The date and time that the syringe was prepared will be recorded on the syringe label along with subject ID
- Syringes will be labeled with the statement "Caution: New Drug—Limited by Federal (or United States) law to investigational use."
- The syringe will be held between 2 to 25°C (36 to 77°F) for up to 12 hours.

9.4 Storage and Stability

Investigational product must be stored separately from normal hospital stocks and must be stored in a securely locked area accessible only to authorized trial personnel until dispensed. The temperature must be monitored and documented on the appropriate form for the entire time that the investigational product is at the trial site. If the storage temperature deviates from the permitted range, the investigational product must not be administered, and the sponsor-investigator should be contacted for additional instruction.

Novavax COVID-19 Vaccine, Adjuvanted unpunctured multi-dose vials may be stored in refrigeration between 2 to 8°C (36 to 46°F). Vaccine must not be frozen and must be protected from light. After the first needle puncture, the vial may be held between 2 to 25°C (36 to 77°F) for up to 12 hours. Discard the vial 12 hours after the first puncture.

9.5 Accountability

The PRC will maintain records of product delivery, site inventory, and product disposal or return. The data coordinating center will verify each site's product accountability records against the record of administered doses in the electronic case report forms (eCRFs), the source documents, and the communication from the online randomization program.

9.6 Dosing and Administration

Study product will be supplied by the PRC as 0.5 mL single-dose, pre-filled syringes. Administer as follows:

- Visually inspect the syringe for particulate matter and/or discoloration prior to administration. If either of these conditions exist, do not administer.
- Gently shake the prefilled syringe.
- Identify the deltoid muscle (upper arm) and cleanse the injection site with alcohol.
- Insert needle (22 to 25 -gauge 1-inch needle recommended; 1 ½ inch needle recommended for those with BMI ≥ 30) at a 90-degree angle to the skin and inject entire contents of the syringe intramuscularly. Do not inject the vaccine subcutaneously or intravenously. Care should be taken to avoid administering the injection into or near blood vessels and nerves.
- Monitor the subject for at least 15 minutes post administration. Monitor for 30 minutes if allergy-related contraindication to another type of COVID-19 vaccine, non-severe immediate (onset within 4 hours) allergic reaction after a previous dose of COVID-19 vaccine or anaphylaxis after non-COVID-19 vaccines or injectable therapies.

10.0 STUDY ASSESSMENT SCHEDULE AND PROCEDURES

10.1 Study Calendar

Procedure (Visit Window)	Visit 1 (V1) (Day 0)	F/U 1 ⁵ (Day 7-15)	Visit 2 (V2) (Day 28-65)	Visit 3 (V3) (V1 + 180 days +/- 30 days)
Informed Consent	X			
Demographics	Χ			
Concomitant Medications	X		Х	Х
Medical History ¹	Χ			
Inclusion/Exclusion Criteria	Х			
Blood draw (Serum & CMI)	X		X	Х
Standard of Care Recombinant COVID-19 Vaccine Booster	X			
7-Day Vaccine Diary ²	X			
SCAI, PDAI, or SCCAI Questionnaire ³	Х		Х	х
Adverse Event Monitoring	Х	Х	Х	Х
Telephone Contact ⁴		Χ		

Notes:

- 1. Baseline medical history included all IBD diagnoses or solid organ transplant diagnoses, medication history, and information in the source documents.
- 2. Dispense the 7-day Vaccine Diary at Visit 1 for subjects to complete at home.
- 3. SCAI, PDAI, or SCCAI will be administered based on IBD diagnosis at visits 1, 2, and 3.
- 4. Between Visit 1 and Visit 2, the study staff will attempt two phone contacts to assess AEs and remind them to complete vaccine diaries as well as to assist with subject retention.
- 5. Visits can be conducted via telephone calls. Patients who don't respond to survey will be emailed and receive a phone call reminding them to fill out diary.

10.2 Study Assessments by Visit

Visit #1 (V1) Baseline/Enrollment Visit (Day 0)

- Obtain written informed consent or remote consent.
- Review the inclusion and exclusion criteria to confirm eligibility.
- Assign Subject ID number.
- Record demographics (gender, age, race and ethnicity)

- Collect medical history, including vaccination history and medications (ongoing and any medications taken during the last 30 days)
- If patient has IBD complete Short Crohn's Activity Index (SCAI), Simplified Pouchitis Disease Activity Index (PDAI), or Simple Clinical Colitis Activity Index (SCCAI)
- Collect a baseline blood sample #1 of approximately 60ml (12 teaspoons)
- Provide study intervention, recombinant NVX-CoV2601 COVID-19 booster.
- If the patient is receiving the standard-of-care blood tests, these additional research samples will be collected at the same time as the standard-of-care tests.
- Subjects will be instructed to contact the study team with any concerns or development of fever, chills, rash, or other concerning symptoms.
- A paper version of the vaccine diary chart is also provided.
- A paper ruler will be provided to measure any swelling or redness.

Follow up Phone Call (Day 7-15)

- 7-15 days after the patient receives the COVID-19 vaccine booster, the patient will be contacted by clinical research coordinator
- Collect information to identify any adverse events including fevers or chills, rash and any unplanned visits to the emergency room or to their primary care physicians.
- Collect vaccine diary (phone) remind patient to fill out if not already filled out.

Visit #2 (V2) Month 1 (Day 28-65) post COVID-19 booster.

- Collect blood sample #2 of approximately 60ml (12 teaspoons)
- Collect SCAI, PDAI, or SCCAI for patients with IBD.
- Ask solid organ transplant recipients if they have been diagnosed with transplant rejection.
- Collect information to identify any adverse effects, including, fever, chills, rash, and any unplanned visits to the emergency room or to their primary care provider.

Visit #3 (V3) (V1 + 180 days +/- 30 days)

- Collect blood sample #3 of approximately 60ml (12 teaspoons)
- Collect SCAI, PDAI, or SCCAI for patients with IBD.
- Ask solid organ transplant recipients if they have been diagnosed with transplant rejection.
- Collect information to identify any adverse effects, including, fever, chills, rash, and any unplanned visits to the emergency room or to their primary care provider.

10.3 Informed Consent Procedures

The informed consent process will be conducted following all federal and institutional regulations relating to informed consent. Informed consent will be obtained prior to conducting any study-related activities.

The informed consent process will be performed as follows:

- Delegated study staff will review the informed consent form and discuss the study in detail with the potential research subject.
- Delegated study staff will explain the study, its risks and benefits, what would be required of the research subject, and alternatives to participation.
- The research subject will be given the opportunity to take the informed consent form home so that they may discuss it with family members, friends, clergy or others when possible.

- The subject will have the opportunity to ask questions and have all questions answered by the delegated study staff and/or PI.
- The informed consent document must be signed and dated by the research subject.
- Delegated study staff will review the informed consent document to ensure that all fields that require a response are complete (i.e., checkbox marked yes or no, etc.) as applicable.
- The research subject will be given a copy of the signed and dated informed consent form. The original signed informed consent form is kept with the subject records.

A research subject will be defined as "enrolled" in the study when they meet the following criteria:

• The subject has been consented by study staff and received the study intervention.

10.4 Clinical assessments

10.4.1 Blood Samples

All subjects participating in the study will have blood specimens collected at three in-person visits. All of these blood specimen collections will be for evaluation of humoral and cell mediated immunity to COVID-19 vaccine. To evaluate humoral immunity we will send samples to LabCorp. They will use a quantitative assay to determine COVID-19 antibodies. We have used these assays in our previous studies evaluating humoral immunogenicity to COVID-19 vaccines. ^{10, 21}

Cell-mediated immunity to COVID-19 will be evaluated at UW. Specimens at UW will be labeled with the subject's study ID number and date of collection so that the data collected for this protocol can be linked to the sample. Samples will be stored in Rennebohm Hall at the University of Wisconsin. Only investigators and key personnel assigned to the laboratory have access to the lab. Samples will be coded (labeled with subject ID and date of collection) before they arrive at the laboratory. All computers used for data storage and analysis are password protected and used exclusively by key personnel.

Blood samples will be stored for future unspecified studies. Participants may withdraw their samples by contacting [name] at any time. Any future studies that will utilize these specimens will be done by UW researchers and will be submitted for a separate IRB approval. Only coded samples and data will be released for future research. Information linking the samples and data to individual participants will not be released.

COVID-19 antibody concentration analysis: These samples will be shipped to LabCorp. They will use LabCorp's Cov2Quant IgG™ assay which uses immunoassay that uses electrochemiluminescent technology (ECL) for quantitative determination of anti-receptor binding domain (RBD) IgG antibodies specific to SARS-CoV-2. The RDB of the spike protein is the moiety that interacts directly with the ACE2 receptor on a host cell to enable viral entry. In addition to RBD being a critical player, it is also poorly conserved among other coronaviruses. Therefore, RBD represents a promising antigen for detecting SARS- antibodies in humans. There is also a strong correlation between levels of RBD-binding antibodies and SARS-COV-2 neutralizing antibodies in patient sera. The results of this assay will be shared with patients as positive or negative rather than the amount of antibody detected. Patients will be asked to follow up with their gastroenterologist or transplant surgeon if they have any questions regarding the test results. We will also use LabCorp Qualitative detection of high affinity antibodies to SARS-CoV-2 nucleocapsid (N) protein, the virus that causes COVID-19, to aid in identifying individuals with an

adaptive immune response to SARS-CoV-2, indicating recent or prior infection. This will be done at every time point.

Cell Mediated Immunity to COVID-19

For each patient, peripheral blood mononuclear cells (PBMCs) will be isolated from green tubes or CPT tubes per study visit, and stored in liquid nitrogen. IFN-Y ELISpot, which detects both CD4 and CD8 T cell effectors, will be used to detect T-cell immunity to the Covid-spike protein or peptides. The plates will be read on an AID ELISpot reader (Cell Technology, Inc., Columbia MD, reader software v.3.1.1.). A positive response to antigen will be defined as a frequency that was significantly (p < 0.05, two-tailed t test) greater than the mean of control no-antigen wells and detectable (i.e., >1:100,000). T cell responses will be correlated to Covid-19 neutralizing antibody responses. We have previously evaluated cell-mediated immunogenicity to COVID-19 vaccine in patients with IBD. ²²

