6.2 Secondary objectives

The vaccine will be evaluated for two seasons, separately: 2023/2024 and 2024/2025. Thus, we will have two co-secondary objectives.

6.2.1 Sustained antibody concentrations of NVX-CoV2601 booster dose/(2024/2025 COVID booster).

We will evaluate sustained antibody concentrations using a quantitative assay from LabCorp, which is currently being used by the Centers for Disease Control and Prevention (CDC) to evaluate seroprevalence and study immunity at six months after completion of the booster dose (V3).

Endpoint:

We will evaluate individuals who are seropositive at V2 and V3 in both groups.

Seropositivity rate at V2 and V3 in all participants.

Seropositive will be defined by positive anti-receptor binding domain (RBD) IgG antibodies specific to SARS-CoV-2 performed by Labcorp (greater than 1.0 in µg/mL).

Success Criterion: Descriptive

6.2.2 Seroconversion.

Percentages (and 2-sided 95% Cis) of participants who were seronegative (less than 1.0 in $\mu g/mL$) at baseline and became seropositive (greater than 1.0 in $\mu g/mL$) after immunization will be evaluated for before and after measures. For initially seropositive subjects at V1, antibody concentration at post-vaccination (V2) \geq 4 fold the pre-vaccination antibody concentration.

Endpoint:

Individuals who achieve seroconversion at V2.

Success Criterion: Descriptive

6.2.3 Cell-mediated immunity to NVX-CoV2601/(2024/2025 COVID booster). **COVID-19** booster vaccine.

We will evaluate cell-mediated immunity to a booster dose vaccine at baseline (V1) and one month after a booster dose (V2) in patients with IBD and solid organ transplant recipients. IFN-Y ELISpot, which detects both CD4 and CD8 T cell effectors, will be used to detect T-cell immunity to the Covid-spike protein or peptides.

Endpoint:

We will evaluate the interferon gamma responses at V2 compared to V1.

An interferon gamma response will be considered any measurable response.

Success Criterion: Descriptive

6.2.4 Sustained cell-mediated immunity to NVX-CoV2601/(2024/2025 COVID booster). **COVID-19 booster vaccine.**

We will evaluate sustained cell-mediated immunity against Covid-spike proteins approximately six months following V1 (V1 + 180 days, +/-30 days) (V3)

Endpoint:

We will evaluate the interferon gamma responses at V3 compared to V1.

Success Criterion: Descriptive

The safety of the vaccine boosters will be assessed for both seasons separately. This includes section 6.3-6.5.

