7.0 STUDY DESIGN

7.1 Program Type / Scope of Study / Clinical Design / Sites

This will be a single-center, prospective, unblinded, non-randomized study of 141 immunosuppressed patients who are planning to receive a NVX-CoV2601 COVID-19 vaccine booster dose as standard of care and are willing to participate in the study. We have paused recruitment in 2023-2024 season due to low recruitment. We are extending the study to enroll an additional 120 immunosuppressed patients who are planning to receive a 2024/2025 COVID-19 vaccine booster dose as standard of care and are willing to participate in the study.

During the 2024/2025 season at least 35 patients will have inflammatory bowel disease and at least 35 patients will be a solid organ transplant recipient. After obtaining informed consent, individuals who meet the inclusion criteria and none of the exclusion criteria will be invited to participate in the study. Blood samples will be collected from each participant at the baseline visit (V1), at 1M post–booster (V2 visit), and 6M post–booster (V3).

Figure 1. Schematic of Visits:

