11.0 DATA HANDLING AND RECORD KEEPING

Data will be stored on a web-based platform to collect all patient-related information, disease activity, and other study questionnaires. This web-based platform will be developed by University of North Carolina. They will not be the data safety monitor for the study.

The University of North Carolina will serve as a Data Management Center (DMC) for this study. The work will be conducted in the Bioinformatics and Biostatistics Core of the Center for Gastrointestinal Biology and Disease (CGIBD). [name], will lead the DMC for this study. The Core has served as the Data Management Center for the Crohn's and Colitis Foundation Clinical Alliance. In that capacity the DMC has conducted a number of randomized trials and observational studies of IBD. They have also served as the Data Management Center for the Sinai Helmsley Alliance for Research Excellence which is a multicenter study of patients with IBD. The DMC will be charged with creating, managing, and housing the data management system.

The DMC will be responsible for all of the data management needs of the study. These activities will include, but not be limited to the following. They will build applications to collect baseline and follow-up data as specified in the protocol, generate reports about recruitment, enrollment, compliance, and dropouts, provide barcodes for biological specimens and build tracking programs for the specimens, provide data sets for analysis, and participate in data analysis and reporting. The only identifiers UNC will have access to are Subject ID numbers and dates of service. They will not have access to linking coded data. The link to the subject ID will be maintained by UW research staff.

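### ELISpot specimens reach the in-house laboratory labelled with subject ID and collection date, and no masking is stated, so staff can infer which sample is pre- and which is post-vaccine

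*Combined protocol and SAP*

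**What the plan says.** Section 10.4.1 places the assay in-house: "Cell-mediated immunity to COVID-19 will be evaluated at UW". On labelling it says "Specimens at UW will be labeled with the subject's study ID number and date of collection", and then: "Samples will be coded (labeled with subject ID and date of collection) before they arrive at the laboratory". Section 11.0 repeats the labelling rule. On access, section 10.4.1 says: "Only investigators and key personnel assigned to the laboratory have access to the lab". It does not say who reads the plates.

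The endpoint in section 6.2.3 is within-person: "We will evaluate the interferon gamma responses at V2 compared to V1". Section 6.2.4 has the parallel V3 against V1 comparison. Both carry a descriptive success criterion. Section 7.1 describes a "single-center, prospective, unblinded, non-randomized study".

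The cell-mediated immunity part of section 10.4.1 has the cells isolated at each visit and frozen in liquid nitrogen. It names an automated ELISpot reader with its software version. A positive response must differ significantly from the no-antigen wells (two-tailed t test, p < 0.05) and exceed 1 in 100,000. Section 6.2.3 is looser and counts any response that can be measured. The antigen is left open, since the assay "will be used to detect T-cell immunity to the Covid-spike protein or peptides", and either of two blood tube types is allowed.

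Among the data management centre's tasks, section 11.0 lists that it will "provide barcodes for biological specimens and build tracking programs for the specimens". It does not connect these barcodes with masking.

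**The concern.** Every participant is vaccinated, so the visit is the exposure and the before/after difference is the whole result. Anyone who handles the assay and can tell the visit can also tell which sample is expected to be higher. The steps that involve judgement are setting up plates, choosing reader settings, accepting or rejecting wells, and deciding on repeats. Any leaning in those steps would tend to favour V2 or V3 over V1, and no comparison group would cancel it. Cell-mediated immunogenicity is named in Aim 1 (section 5.2), so the comparison matters to the study's message although it is secondary.

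**Working it through.** The plan states no power, significance level or effect size for the ELISpot comparison (section 12.1 says that no formal sample size was calculated). There is therefore no figure to reproduce. The check has three steps.

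**1. Does the label allow the visit to be inferred?** Inputs are the visit windows in sections 10.1 and 10.2.
- V1 = day 0; V2 = day 28 to 65; V3 = 180 ± 30 = day 150 to 210.
- Gap from V1 to V2: 28 to 65 days.
- Gap from V2 to V3: smallest 150 − 65 = 85 days; largest 210 − 28 = 182 days.

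The windows do not overlap. Two or more in-window tubes with the same subject ID can be put in time order from their labels, and a full set of three identifies V1, V2 and V3. A single tube cannot be placed without a second tube or the vaccination date.

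**2. Does anything else in the plan close the gap?**
- Masking of laboratory staff, concealed plate order, or one participant's visits kept on one plate: none stated.
- Automated reader and numeric positivity rule (section 10.4.1): stated, and they reduce discretion.
- Reader settings, rules for rejecting wells, rules for repeats: none stated.
- Definition of response: two are given, a numeric one in section 10.4.1 and a looser one in section 6.2.3.
- Barcodes (section 11.0): planned for tracking. The link to the subject ID is kept by UW research staff.

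**3. How much does one misclassified participant matter?** The synopsis gives 21 enrolled; section 12.1 gives 20.
- Shift in response rate per participant = 100 / N: 100 / 21 = 4.8 points, or 100 / 20 = 5.0 points.
- Illustration at N = 21, where the count is an assumption: 1 participant gives 4.8 points, 2 give 9.5, and 6 give 28.6.
- If every changed pair goes the same way, the exact two-sided paired p-value is 2 × 0.5^d. For d = 4 it is 0.125, for d = 5 it is 0.0625, and for d = 6 it is 0.031.

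These figures show sensitivity only. They do not estimate how many readings would be affected.

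**The case against.** The strongest reply is that the assay is already fairly objective and little depends on it. An instrument reads the plates, positivity has a numeric threshold, the endpoints are secondary with no success decision attached, and section 12.1 calls the results descriptive and exploratory. The primary antibody endpoint is measured externally at LabCorp. Antigen preparation, tube type and plate allocation are often left to laboratory procedures. All of this stands as a limit on the importance of the point. It does not close the gap, because the open steps lie before and after the instrument's count, and the looser definition in section 6.2.3 sets aside the numeric rule.

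Three stronger readings are tempting, and the documents do not support them.
- A reader might infer that plate readers know the visit. The label shows a date and not a visit, and the documents do not say who reads the plates or whether anyone compares tubes. They support only that visit order can be inferred.
- A reader might infer that the planned barcodes would in themselves remove the problem. They are planned for tracking. They mask only if they replace the readable ID and date, and if plate readers cannot see the key. Nor would they settle antigen preparation or plate allocation.
- A reader might infer that one or two misread samples could create a statistically significant result. Nothing in the documents gives a rate of misreading. On an exact paired test, six one-way changes among 21 participants would be needed to fall below 0.05.

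**Conclusion.** The point holds as an avoidable weakness in how a secondary endpoint is measured. The labelling rule lets laboratory staff infer pre- and post-vaccine samples in a comparison where the visit is the exposure, and no masking is stated. The instrument and the positivity rule narrow the scope for bias without removing it. The size of any bias is unknown; what is known is that each misclassified participant shifts the response rate by about 4.8 points at N = 21. This rests on the visit windows being kept, on staff seeing more than one tube from a participant or knowing the vaccination date, and on no separate laboratory procedure that masks the samples, since the documents mention none. The primary endpoint is not affected. The change is worth making because it is cheap, but no success decision depends on it.

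**What to change.** The synopsis reports 21 participants enrolled and no further recruitment. Section 10.3 defines enrolment as having received the vaccine, and section 10.2 has baseline blood drawn at that same visit. The baseline samples have therefore been collected under the current rule, so the change belongs at plating and not at collection. The documents do not say whether assays have been run.

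For assays not yet run, amend sections 10.4.1 and 11.0 as follows.
- Recode the stored vials before plating with visit-neutral codes as the only label that laboratory staff can see. The data management centre's barcodes can serve.
- Hold the key outside the laboratory, and release visit identity only when plate reading and well acceptance are final.
- Run each participant's V1, V2 and V3 samples on one plate, in an order concealed from the laboratory, with the same antigen preparation.
- Fix reader settings and well-exclusion rules in writing beforehand, and state which of the two response definitions applies.

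For assays already run, report the lack of masking as a limitation of the cell-mediated results.

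The cost is the work of recoding stored vials and drawing up a plate map, and label queries would have to go through the key holder. No new participants or blood samples are needed, and because the cells are frozen, testing a participant's visits together is practicable.
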